### 9.1 Target BG Challenges

All subjects will take part in the target blood glucose (BG) challenges (Table 4: Target BG Challenges). Following the commencement of the hybrid closed-loop phase, subjects will be required to set their target BG to 130 mg/dL for approximately 72 hours for days 1-3, 140 mg/dL for days 4-6, and 150 mg/dL for

day 7-9 according to Table 4: Target BG Challenges. Upon completion of the 3 target BG challenges (130 mg/dL, 140 mg/dL, and 150 mg/dL), subjects may choose their desired target BG between 110-150 mg/dL for the remainder of the 5-days of the hybrid closed-loop phase.

**Table 4: Target BG Challenges**

	Days									
	1	2	3	4	5	6	7	8	9	10-14
Target BG	130 mg/dL			140 mg/dL			150 mg/dL			110-150 mg/dL

These settings will be reviewed by clinical staff at scheduled visits and through the remote monitoring system to ensure the requirements are met. If the requirements have not been met, clinical staff may request the subject adjust their setpoint until the requirements are met unless there are safety concerns.

## 9.2 Hotel/Rental House Environment

The subset of subjects participating in the hotel/rental house environment will be encouraged to eat meals of their own choosing, unrestricted in carbohydrates, and to engage in moderate intensity exercise for a minimum of 1 hour per day.

Moderate intensity exercise is defined using the CDC guidelines:

**Table 5: CDC Guidelines for Moderate Intensity Exercise**

	Children and Adolescents	Adults	Older Adults
Moderate Intensity Activities	Brisk walking Bicycling Hiking Catching/throwing	Walking/jogging 2.5 miles per hour Bicycling Aerobics	Walking/hiking Jogging Bicycling Aerobics

## 9.3 Visit 4

**Visit 4** represents the commencement of the hybrid closed-loop phase. For subjects in Group 1, this visit will be conducted at the hotel/rental house. For subjects in Group 2 this visit will be conducted at the clinical study site. All scheduled assessments will be performed according to Table 2: Schedule of Assessments. This visit will include:

- Pregnancy test for women of childbearing potential
- Review of concomitant medications
- Average total daily insulin (approximately over the past 7 days)
- Average total daily basal insulin (approximately over the past 7 days)
- Average total daily bolus insulin (approximately over the past 7 days)

- Pump settings/MDI dosing
- Assessment of AEs
- Remote monitoring initiation
- Omnipod Horizon™ System device training conducted by trained clinical site staff
  - Subjects will be trained on operating Omnipod Horizon™ in both Manual and Automated Modes.
  - This will include first time device set-up with entry of basal profile, bolus calculator settings with insulin:carbohydrate ratio, target glucose and correction factor.
  - The Pod will be filled with the subject's own U-100 rapid-acting insulin and placed on body. Subjects will also be trained on use of Dexcom G6 CGM, regardless of previous experience, setting up low (recommended to be 70 mg/dL or higher) and high glucose alerts (recommended to be 300 mg/dL or lower) and entering transmitter serial number into the Horizon App.
  - In addition, Omnipod Horizon™ has a novel bolus calculator feature that incorporates both the CGM value and trend into the suggested bolus amount. In general, if the CGM values are trending up or down, the calculator will add or subtract insulin from the suggested bolus amount to help keep BGs within target range.
- Dispense Omnipod Horizon™ System
- Complaints/device deficiencies for CGM, BG and ketone meter
- Device uploads for CGM, BG and ketone meter
- Data review by clinician
- Removal of the subject's personal insulin pump (if applicable)
  - Prior to commencing hybrid closed-loop, the subject's personal insulin pump will be removed, if applicable. Investigators may use the Insulet-provided Patient Therapy Order Form (PTOF) as a guide to transition subjects from MDI to pump therapy (Appendix).

At the conclusion of the training and completion of assessments, each subject will initiate their treatment marking their commencement of the hybrid closed-loop phase.

#### 9.4 Visit 5

**Visit 5** will be conducted in the hotel/rental house for subjects in Group 1, and over the telephone for subjects in Group 2. All scheduled assessments will be performed according to Table 2: Schedule of Assessments. This visit will include:

- Review of concomitant medications
- Assessment of AEs since last visit
- Complaints/device deficiencies such as occlusion alarms and system hazard alarms since last visit
- Device uploads for BG and ketone meter
- Data review by clinician

## 9.5 Visit 6

**Visit 6** will be conducted in the hotel/rental house for subjects in Group 1, and over the telephone for subjects in Group 2. All scheduled assessments will be performed according to Table 2: Schedule of Assessments. This visit will include:

- Review of concomitant medications
- Assessments of AEs since last visit
- Complaints/device deficiencies such as occlusion alarms and system hazard alarms since last visit
- Device uploads for BG and ketone meter
- Data review by clinician

Subjects in Group 1 will be discharged home on study day 3 (Visit 6).

During each visit, subjects will be reminded to set the appropriate target BG on the appropriate day as applicable.

## 9.6 Visits 7, 8 and 9

**Visits 7 through Visit 9** will be conducted over the telephone. All scheduled assessments will be performed according to Table 2: Schedule of Assessments. These visits will include:

- Review of concomitant medications
- Assessment of AEs since last visit
- Complaints/device deficiencies such as occlusion alarms and system hazard alarms since last visit
- Device uploads for BG and ketone meter (if visit is conducted at the clinical study site)
- Data review by clinician
- Ensuring at least 72 hours of data collected at designated target BG levels per Table 4 – Target BG Challenges.

During each visit, subjects will be reminded to set the appropriate target BG on the appropriate day as applicable.

## 9.7 Visit 10 (End of Study)

**Visit 10** will be conducted in person at the clinical study site. All scheduled assessments will be performed according to Table 2: Schedule of Assessments. If the subject has not experienced any serious adverse events, and continue to meet eligibility requirements, the subject will be deemed eligible to participate in the pivotal study. This visit will conclude their participation in the prepivotal study. This visit will include:

- Review of concomitant medications
- Height
- Weight

- Assessment of vital signs
- Assessment of AEs since last visit
- Completion of questionnaires (see Table 3: Questionnaires for specific requirements by age group) :
  - WHO-5
  - EQ-5D
  - T1DDS
  - DTSQc
  - Hypoglycemia Confidence Scale
  - HABS
  - PSQI
  - IDSS (T1)
  - SUS
  - PAID-(Teen, Child)
  - INSPIRE-(Adult, Youth, Parent)
    - Used to measure a caregiver's experience of the support they receive
  - Clarke
  - Human Factors (HF) Questionnaire
    - Measures trust in the Horizon™ System
- Discontinuation of remote monitoring
- Return study devices (Omnipod Horizon™ System, CGM, BG and ketone meters if not extending into pivotal study)
- Complaints/device deficiencies such as occlusion alarms and system hazard alarms since last visit
- Device uploads for BG and ketone meter
- Data review by clinician

For subjects not extending their participation into the pivotal study, they will return their study devices to the site and their participation in the study will end.

## 9.8 Unscheduled Visits

Aside from scheduled visits, subjects may require an unscheduled visit either by telephone or in person at the clinical study site. All scheduled assessments will be performed according to Table 2: Schedule of Assessments. This visit will include, at a minimum:

- Review of concomitant medications
- Assessment of vital signs (if visit is conducted at the clinical study site)
- Assessment of AEs since last visit
- Complaints/device deficiencies such as occlusion alarms and system hazard alarms since last visit
- Device uploads for BG and ketone meter (if visit is conducted at the clinical study site)
- Data review by clinician

Additional assessments may be warranted at the discretion of the investigator.

Instructions will be given to subjects on how to contact clinical study staff 24 hours per day to report any study related problems. Subjects will be encouraged to call the clinical study site at any time with any concerns.

## 9.9 Early Withdrawal

Any subject may withdraw early from the study at any time for any reason. Upon withdrawal, assessments will be performed following the Table 2: Schedule of Assessments. The investigator may also terminate a subject's participation in the study if it is in the best interest of the subject or if the Sponsor or local regulatory agency (e.g., FDA) terminates the study.

The Early Withdrawal visit will include:

- Review of concomitant medications
- Height
- Weight
- Assessment of vital signs
- Assessment of AEs since last visit
- Completion of questionnaires (see Table 3: Questionnaires for specific requirements by age group):
  - WHO-5
  - EQ-5D
  - T1DDS
  - DTSQc
  - Hypoglycemia Confidence Scale
  - HABS
  - PSQI
  - IDSS (T1)
  - SUS
  - PAID-(Teen, Child)
  - INSPIRE-(Adult, Youth, Parent)
  - Clarke
  - Human Factors (HF) Questionnaire
- Discontinuation of remote monitoring
- Return all study devices
- Complaints/device deficiencies such as occlusion alarms and system hazard alarms since last visit
- Device uploads for BG and ketone meter
- Data review by clinician

The reasons for withdrawal will be recorded, and the subject's participation in the study will end.

In the event of a subject's death during the study, the subject's participation will be considered terminated and the date of death will be used as the date of study exit.

## 9.10 Lost to Follow-up

Every effort will be made to contact a subject in the event of a missed scheduled visit. A subject will be considered lost to follow-up if they are inaccessible by two or more different methods of contact and fail to show up for two scheduled visits. The site will document each attempt made to contact the subject and specify the reason for early withdrawal as lost to follow-up.

## 10 SPONSOR REPRESENTATIVES

One or more representatives of the Sponsor may be present at the hybrid closed-loop clinical study site visits under supervision of the investigator.

## 11 SAFETY

### 11.1 Types of Known Risks and Benefits

There are known risks and benefits. Most of the risks are not unique to the study and are typical for patients using insulin pumps, CGM, and BG meters.

The known risks are as follows:

- Hypoglycemia and/or hyperglycemia as a result of change in diet, activity, diabetes management or insulin regimen during the study.
- Hypoglycemia, hyperglycemia, diabetic ketoacidosis, seizure, coma or death related to insulin administration, pump use or misuse, or Horizon™ System use or misuse.
- Use of the Pod (Omnipod® tubeless, insulin delivery pump) - Because the Pod uses only rapid-acting insulin, users are at increased risk for developing hyperglycemia if insulin delivery is interrupted. If it is untreated, prolonged hyperglycemia can quickly lead to diabetic ketoacidosis (DKA). DKA can cause symptoms such as breathing difficulties, shock, coma, or death. Further, occlusions can interrupt insulin delivery and lead to hyperglycemia or DKA. Other potential risks associated with using the Pod are:
  - Anaphylaxis (allergic shock)
  - Bruising at the Pod site
  - Bleeding at the Pod site
  - Erythema (redness at the Pod site)
  - Excoriation (raw skin at Pod site)
  - Pruritus (itching)
  - Induration (hardening of the skin at the Pod site)
  - Infection (can include heat, redness, swelling, pain, and drainage)
  - Inflammation (redness, swelling)
  - Skin reaction to adhesive at the Pod site
  - Papule (small, solid raised area on the skin similar to a pimple)
  - Pain or discomfort

- Ulceration (skin sores)
- Vesicles (blisters)
- Use of the CGM - risk of bruising, infection, pain and/or bleeding at the site of insertion, and skin site reaction to adhesive.
- On rare occasions, the CGM sensor may break and leave a small portion of the sensor under the skin that may cause redness, swelling, or pain at the insertion site, and may require surgical removal.
- Blood sampling with fingerstick - minor discomfort and risk of infection at site of fingerstick.

There are several potential benefits from this study. The Omnipod Horizon™ System is designed to provide automated glucose control. The system is expected to reduce hypoglycemia without incurring an unacceptable increase in hyperglycemia and mean glucose. The system is also expected to reduce the extent and magnitude of hyperglycemia associated with meals. The Omnipod Horizon™ System uses a control-to-target strategy that attempts to achieve and maintain a set target glucose level.

## 11.2 Hypoglycemia/Hyperglycemia

Subjects will be asked to treat per their usual routine if they suspect either hypoglycemia or hyperglycemia, either by confirmation of hypoglycemia with a fingerstick BG, symptoms, or perceived risk.

Subjects will be encouraged to manage their hyperglycemia per their usual routine. This includes checking for ketones using the study-approved ketone meter and administering a correction bolus if needed.

In the event of unexplained hyperglycemia, where the CGM is  $>300\text{mg/dL}$  for 1h or  $>250\text{ mg/dL}$  for 2h, blood glucose (measured with BG meter) and ketones should be checked. If BG is  $\geq300\text{ mg/dL}$  and ketones are  $>1.0\text{ mmol/L}$ , an occlusion or dislodged cannula should be suspected. The Pod should be removed, and the subject will be instructed to replace the Pod. Subjects should contact the clinical site for further instructions to determine whether an additional injection of insulin is required. This prolonged hyperglycemic event, defined as meter BG  $\geq300\text{ mg/dL}$  and ketones  $>1.0\text{ mmol/L}$ , will be recorded as an adverse event and cause may be attributed to suspected occlusion if the cannula is in situ or dislodged cannula if it has been pulled out. Pods will be requested to be returned to Insulet for analysis. An Adverse Event form will be completed per the Reportable Adverse Events section below.

## 11.3 Adverse Events

### 11.3.1 Definitions

**Adverse Event (AE):** is defined as any untoward medical occurrence, unintended disease or injury, or any untoward clinical signs (including an abnormal laboratory finding) in subjects, users or other persons, whether or not related to the investigational medical device.

NOTE 1: This includes events related to the investigational medical device or the comparator.

NOTE 2: This definition includes events related to the procedures involved (any procedure in the clinical investigation plan).

**Serious Adverse Event (SAE):** Any untoward medical occurrence that:

- Led to death
- Led to serious deterioration in the health of the subject, that either resulted in:
  - a life-threatening illness or injury, or
  - a permanent impairment of a body structure or a body function, or
  - in-patient or prolonged hospitalization, or
  - medical or surgical intervention to prevent life-threatening illness or injury or permanent impairment to a body structure or a body function.
- Led to fetal distress, fetal death, or a congenital abnormality or birth defect.

NOTE: Planned hospitalization for a pre-existing condition, or a procedure required by the clinical investigational plan, without serious deterioration in health, is not considered a serious adverse event.

**Unanticipated Adverse Device Effect (UADE):** Any serious adverse effect on health or safety or any life-threatening problem or death caused by, or associated with, a device, if that effect, problem, or death was not previously identified in nature, severity, or degree of incidence in the investigational plan or application (including a supplementary plan or application), or any other unanticipated serious problem associated with a device that relates to the rights, safety, or welfare of participants.

**Adverse Device Effect (ADE):** An adverse device effect is an adverse event related to the use of an investigational medical device.

NOTE 1: This definition includes any adverse event resulting from insufficient or inadequate instructions for use, deployment, implantation, installation, or operation, or any malfunction of the investigational medical device.

NOTE 2: This definition includes any event resulting from user error or from intentional misuse of the investigational medical device.

**Serious Adverse Device Effect (SADE):** A serious adverse device effect is defined as an adverse device effect that has resulted in any of the consequences characteristic of a serious adverse event.

**Device Deficiency (DD):** A device deficiency is defined as a device related complaint or malfunction or any inadequacy of a device with respect to its identity, quality, durability, reliability, safety or performance and includes misuse or use errors and inadequate labeling. A device deficiency is something that happens to a device or is related to device performance, whereas an adverse event happens to a participant. A device deficiency may occur independently from an AE, or

along with an AE. An AE may occur without a device deficiency or there may be an AE related to a device deficiency.

Note: for reporting purposes, sites will not be asked to distinguish between device complaints and malfunctions.

For any event where there is suspicion that the study device is involved, the Sponsor will request that the investigator return the device for evaluation.

All device complaints or malfunctions involving any investigational component of the Omnipod Horizon™ System used in the study will be reported to the Sponsor within 5 business days of knowledge of the deficiency and documented on an appropriate eCRF. All study product associated with a reported device deficiency (PDM, Pod, and CGM) should be retained at the clinical site and returned to the Sponsor or CGM manufacturer for investigation and analysis.

### **11.3.2 Reportable Adverse Events**

Adverse events will be assessed on an ongoing basis throughout the study. Adverse event reporting will begin at the start time of the standard therapy phase (i.e., insertion of the CGM sensor) and continue through the hybrid closed-loop phase until the subject's participation has ended. All adverse events must be followed until resolution, or until the AE has stabilized, or until the study has been completed.

Pre-existing medical conditions or symptoms observed prior to the start time of the standard therapy phase will not be recorded as an AE and should be collected in the subject's medical history. In the event there is a change (i.e., worsening) in the pre-existing medical condition or symptoms after enrollment meeting the criteria of a reportable adverse event, then an AE must be reported.

For this protocol, a reportable adverse event includes any untoward medical occurrence that meets one of the following criteria:

1. An SAE
2. An ADE unless excluded from reporting in Hypoglycemic Events and Hyperglycemic/Ketotic Events sections below
3. An AE occurring in association with a study procedure
4. An AE not related to a study device issue which leads to temporary or permanent discontinuation of the study device
5. An AE that affects the participant's ability to complete any study procedures
6. An AE for which a visit is made to a hospital emergency department
7. Hypoglycemic Events as defined below
8. Hyperglycemic/Ketotic Events as defined below.

Skin reactions from sensor or pod placement are only reportable if severe and/or required treatment.

For the purpose of this protocol, mild symptoms of hypoglycemia and hyperglycemia (i.e., clinically non-significant) or blood glucose values out of the normal range (whether or not they resulted in delayed meals or correction boluses) will not be reported as AEs unless determined to meet the reportable criteria in the Hypoglycemic Events and Hyperglycemic/Ketotic Events sections below.

All reportable AEs—whether volunteered by the participant, discovered by study personnel during questioning, or detected through physical examination, laboratory test, or other means—will be reported on an AE eCRF.

### **11.3.3 Hypoglycemic Events**

Hypoglycemia is only reportable as an adverse event when one of the following criteria is met:

- Severe Hypoglycemia: The event required assistance of another person due to altered consciousness, and required another person to actively administer carbohydrate, glucagon, or other resuscitative actions. This means that the participant was impaired cognitively to the point that he/she was unable to treat himself/herself, was unable to verbalize his/her needs, was incoherent, disoriented, and/or combative, or experienced seizure or loss of consciousness. These episodes may be associated with sufficient neuroglycopenia to induce seizure or loss of consciousness. If plasma glucose measurements are not available during such an event, neurological recovery attributable to the restoration of plasma glucose to normal is considered sufficient evidence that the event was induced by a low plasma glucose concentration.
- Hypoglycemia resulting in an SAE that may not otherwise meet the definition of Severe Hypoglycemia defined above.

When a hypoglycemic event meets the above reporting requirements, an Adverse Event Form should be completed. A severe hypoglycemia event should be considered a serious adverse event and follow the SAE reporting requirements.

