### **11.9 Medical Monitor**

An independent Medical Monitor will be responsible for individual and timely review of adverse events as defined below. The Medical Monitor will be a physician with relevant therapeutic and medical expertise that is not participating as an Investigator in the study and does not have a financial, scientific, or other conflict of interest with the clinical study.

Specific responsibilities of the Medical Monitor include:

- Review of all adverse events reported during the study
- Review all serious study procedure-related and/or investigational device-related adverse events to determine if the adverse event warrants consideration as a UADE and facilitate the reporting of UADEs if applicable
- Adjudicate the following(a) all SAEs; (b) any events of Diabetic Ketoacidosis or Severe Hypoglycemia; (c) all AEs reported by the site as related or possibly related to the investigational device; and/or (d) any additional events as requested by the Sponsor or DSMB.
- The specified events will be adjudicated to determine:
  - event relatedness to the study procedures and/or the investigational device
  - event categorization and assess seriousness and severity
  - whether an adverse event is anticipated or unanticipated

The adjudication decision of the Medical Monitor will be used for the final classification of events, including relatedness to the study procedures and/or the investigational device, for the determination of safety endpoints and for all regulatory reports, product labeling, and publications or presentations.

The Medical Monitor's roles and responsibilities are described in the Safety Management Plan (SMP).

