### 5.5 EVALUATION OF DEVICE DEFICIENCIES

Device deficiencies will be tabulated and listed in a manner similar to the methods described for adverse events. Any device deficiency leading to an adverse event or study termination will be listed separately.

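### A self-treated low caused by a device malfunction is not reportable as an adverse event, while non-serious hyperglycemia from a suspected Pod failure is

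*Protocol*

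**What the plan says.** Protocol 11.3.1 counts as an adverse device effect (ADE) any adverse event arising from, among other things, inadequate instructions "or any malfunction of the investigational medical device". Item 2 of the reportable events in Protocol 11.3.2 is "An ADE unless excluded from reporting in Hypoglycemic Events and Hyperglycemic/Ketotic Events sections below". The ADE rule therefore gives way to the two sections that follow it.

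For low glucose, Protocol 11.3.3 opens with "Hypoglycemia is only reportable as an adverse event when one of the following criteria is met" and lists two criteria. The first is severe hypoglycemia, which needs another person's active help. On seriousness the section adds: "A severe hypoglycemia event should be considered a serious adverse event and follow the SAE reporting requirements". The second is "Hypoglycemia resulting in an SAE that may not otherwise meet the definition of Severe Hypoglycemia defined above".

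For high glucose, Protocol 11.3.4 lists four criteria: DKA; care at a health facility, or guidance given after the participant contacts the site; meter BG of at least 300 mg/dL with ketones above 1.0 mmol/L; and hyperglycemia resulting in an SAE. It adds that events short of DKA will generally not be serious. Protocol 11.2 says of the BG-plus-ketones event that it "will be recorded as an adverse event and cause may be attributed to suspected occlusion if the cannula is in situ", or to a dislodged cannula if it has come out.

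Downstream, Protocol 12.6.1 and SAP 5.4 tabulate reported adverse events by seriousness and relationship to the device. Item (c) of the Medical Monitor's adjudication list in Protocol 11.9 covers "all AEs reported by the site as related or possibly related to the investigational device". SAP 5.5 states: "Any device deficiency leading to an adverse event or study termination will be listed separately".

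**The concern.** Too much insulin is a central hazard of a system that doses automatically. It could come from over-delivery or from dosing on a wrong glucose value. The study is meant to look at safety under closer supervision before the pivotal study starts (Protocol 1), and the DSMB's view decides whether pivotal enrollment may proceed (SAP 2.5).

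Under the reporting rules, a Pod fault that under-delivers can appear as a non-serious adverse event with a device cause. A fault that over-delivers and causes a low that the subject treats alone cannot. A reader of the device-related tables could then see glycemic harm from failed delivery and none from excess delivery, and could not tell whether none occurred or none was collected.

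**Working it through.** The documents give no figure on this point, and the sample size is not hypothesis-driven, so there is nothing to reproduce. The check is a reading of the rules in order, followed by two illustrations.

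1. **Is a low caused by a malfunction an ADE?** Yes, by Protocol 11.3.1.
2. **Does the ADE item make it reportable?** Only if 11.3.3 does not exclude it (11.3.2, item 2).
3. **Does 11.3.3 exclude it?** Criterion 1 is serious by rule and criterion 2 requires an SAE. Criteria that can admit a non-serious event: 0 of 2, with no device-fault exception.
4. **Same question for highs in 11.3.4.** DKA is serious by rule and the last criterion requires an SAE. The facility-or-guidance criterion and the BG-plus-ketones criterion can both be met without seriousness: 2 of 4. A participant who calls the site about a high and receives guidance has a reportable event. The same call about a low does not create one.
5. **Is there another door in 11.3.2?** Item 4 (device discontinuation) is limited to events not related to a device issue, so it does not help. Items 3 (study procedure), 5 (ability to complete procedures) and 6 (emergency department visit) have no exclusion clause and might admit some non-serious lows. That conflicts with the word only in 11.3.3. A low treated at home without further consequence meets none of these items.
6. **What follows for that low?** There is no adverse event form, so it has no row in the tables of Protocol 12.6.1 and SAP 5.4 and no routine adjudication under item (c) of 11.9. The malfunction is still a device deficiency, but the listing of deficiencies that led to an adverse event probably has nothing to link it to.

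**How often would the permitted hypoglycemia rows be filled?** Inputs: 36 evaluable subjects, 14 days, and the 4% to 7% severe hypoglycemia frequencies in Protocol Table 6. The table gives no reference period T, so 365 and 90 days are both assumed.

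- Expected subjects = 36 × [1 − (1 − p)^(14/T)]. Chance of at least one = 1 − (1 − p)^(504/T), where 504 = 36 × 14.
- T = 365: 0.06 to 0.10 expected; chance 5.5% to 9.5%.
- T = 90: 0.23 to 0.40 expected; chance 20% to 33%.
- At the first DSMB review (16 subjects, at least 10 days, taken as 10), 16 × [1 − (1 − p)^(10/T)] gives 0.02 to 0.03 for T = 365 and 0.07 to 0.13 for T = 90.

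Table 6 counts loss of consciousness or seizure, which is narrower than 11.3.3, so these figures may be low. Excluding anyone with severe hypoglycemia in the past 6 months works the other way. Under either period the rows are more likely empty than not.

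**Would the CGM endpoints show it?** Suppose, purely as an assumption, that 5 of 36 subjects each have one 30-minute device-caused low below 54 mg/dL. Each affected subject gains 30/(14 × 1,440) = 30/20,160 = 0.15 percentage points. The mean over 36 rises by 5 × 0.149/36 = 0.02 points (0.04 for 60-minute lows). The count is invented, and the result shows only that a cohort mean with no cause attached is a poor substitute for an event record.

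**The case against.** The strongest reply is that the plan states its reporting scope openly and has several other ways of catching an over-delivery fault.

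- **The malfunction is not hidden.** Protocol 11.3.1 requires complaints and malfunctions of investigational components to reach the sponsor within 5 business days. They are tabulated and listed under Protocol 12.6.2 and SAP 5.5. The exceptions in Protocol 11.4 do not name over-delivery or dosing on a wrong value, and the DSMB's data may include deficiency listings.
- **Adjudication is possible.** Item (d) of Protocol 11.9 lets the sponsor or DSMB request it for further events.
- **Lows are watched.** Sites are texted at sensor glucose below 55 mg/dL, or below 70 mg/dL for 20 minutes (Protocol 3.1). The sponsor reviews controller data for anomalies (Protocol 12.5, SAP 7.8).
- **The listing might still show the link.** SAP 5.5 speaks of an adverse event, not a reportable one, and the deficiency form is not in the documents.
- **The hyperglycemia rule is not a device-failure rule.** BG plus ketones counts whatever the cause, and mild symptoms and out-of-range values are excluded in both directions.

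All of this stands, and it limits the point. None of it creates an adverse event record for a device-caused, self-treated low: the alerts prompt contact, the controller review looks for anomalies, and item (d) needs someone to know of the event and ask. Alerts based on the sensor could also miss a low when the fault is a falsely high sensor value.

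A reader might infer that the safety data count device harm in one direction only, that such a low can never reach the Medical Monitor, or that the safety endpoints are biased. The documents support none of these. Skin reactions that are severe or treated remain reportable, items 3, 5 and 6 of 11.3.2 may let in some non-serious lows, and item (d) exists. The safety endpoints count only serious device-related events, severe hypoglycemia and DKA.

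**Conclusion.** The point holds in a limited form. The text sets different entry levels for non-serious glycemic events (0 of 2 criteria for lows, 2 of 4 for highs) and makes no exception when a malfunction caused the low. Such an event stays out of the descriptive device-related adverse event tables and out of routine adjudication, and its link to the malfunction is likely missing from the deficiency listing. The primary and secondary safety endpoints, the reporting of the malfunction itself and the CGM endpoints are unaffected.

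The number of events lost cannot be derived from the documents. The conclusion assumes that sites apply the word only in 11.3.3 literally, and that the deficiency form does not separately record a resulting low. The expectation that the permitted rows will most likely be empty also depends on the period assumed for Table 6. This is a traceability gap worth closing cheaply, not a flaw that changes the study's main safety result.

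**What to change.** Add a third criterion to Protocol 11.3.3, cross-referenced in item 2 of 11.3.2: hypoglycemia that the investigator judges related or possibly related to a reported or suspected device deficiency is a reportable adverse event, whatever its severity. All other non-severe hypoglycemia stays excluded.

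Set no fixed CGM cut-off. A sensor threshold could miss the case where the fault is a wrong sensor value. Such events would then pass to adjudication under item (c) of 11.9, to the tables in SAP 5.4 and to the listing in SAP 5.5 without further change.

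In the same edit, reconcile the word only in 11.3.3 with items 3, 5 and 6 of 11.3.2, so that sites know whether, for example, a non-serious low with an emergency department visit is reportable.

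The cost is a protocol wording change and a few more adverse event forms and adjudications, limited to events with a suspected device fault. Only reporting changes; treatment does not.
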